# 3.1.2. Full Analysis Set

The **Full Analysis Set (FAS)** will include all subjects who (1) are randomized into the study, (2) have received at least 1 dose of study drug, (3) are not HIV positive on Day 1 (defined as subjects with either a) negative Covance antibody test results at first post baseline assessment or b) negative local lab Day 1 rapid test), and (4) in order to contribute to the efficacy analyses of HIV infection, should have at least one post-baseline HIV laboratory assessment (from either local or central laboratory).

Of note, negative Covance antibody test results are defined as either (1) a negative HIV Screening antibody test result or (2) a positive Screening antibody test plus a negative discrimination antibody test result. Subjects will be grouped according to the treatment to which they were randomized.

The FAS is the primary analysis set for efficacy analyses.

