Last Dose Date (OLE phase) is defined as the latest of the OLE phase study drug end dates recorded on the "Extension Phase" Study Drug Administration eCRF with "Permanently Withdrawn" box checked for subjects who prematurely discontinued study drug according to the "Extension Phase" Study Drug Completion eCRF. This date will only be available for subjects treated in the OLE phase of the study. If the last dose date is missing for subjects who prematurely discontinued study drug in the OLE phase of the study, the latest of nonmissing OLE phase study drug start dates and end dates, the clinical visit dates, and the laboratory visit dates, excluding the date of 30-day follow-up visit, from the OLE phase data, will be used to impute the OLE phase last dose date.

**Last Study Date** is the latest of the randomized or OLE phase (if available) study drug start dates and end dates, the clinic visit dates, and the laboratory visit dates, including the 30-day follow-up visit date, for subjects who prematurely discontinued study or who completed study according to the Study Completion eCRF.

Last At-Risk of HIV Infection Date (DB phase) is (1) the date of HIV infection diagnosis as defined in Section 6.2.2 for subjects who have been diagnosed as infected with HIV during the DB phase or (2) the date of the last post-baseline HIV laboratory test (either local rapid or Covance HIV laboratory tests, including the 30-day follow-up visit date) during the DB phase for subjects who have not been infected with HIV during the DB phase.

Last At-Risk of HIV Infection Date (OLE phase) is (1) the date of HIV infection diagnosis as defined in Section 6.2.2 for subjects who have been diagnosed as infected with HIV during the OLE phase or (2) the date of the last post-baseline HIV laboratory test (either local rapid or Covance HIV laboratory tests, including the 30-day follow-up visit date) during the OLE phase for subjects who have not been infected with HIV.

**Baseline value** is defined as the last value obtained on or prior to Study Day 1 for each phase for all assessments, except for DXA BMD. The baseline value for DXA BMD is defined as the last value obtained on or prior to Study Day 14 of each phase.

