# 3.8.2. Analysis Windows

Subject visits might not occur on protocol specified days. Therefore, for the purpose of analysis, observations collected from the DB phase of the study (ie, DB phase data) will be assigned to analysis window. Observations collected from the OLE phase of the study (ie, OLE phase data) will not have analysis window assigned and will be included in listings with derived visit marked as "Extension".

The CASI questionnaire assessment consists of different versions of the questionnaire corresponding to 3 different time periods: screening, baseline and follow-up. All versions of the CASI questionnaire include questions regarding number of sexual partners. For the CASI Screening questionnaire items regarding the number of sexual partners in the last 90 days, the analysis windows are defined as prior to the first dose date. For the CASI Baseline questionnaire items, the analysis windows are defined up to or on the first dose date.

Aside from the number of sexual partners, other items collected in the CASI Screening questionnaire are unique to the screening questionnaire and collected only once (including education, circumcision, drug use, management of HIV risk, etc.) All of these other CASI Screening questionnaire items will be summarized for the Screening visit without applying an analysis window.

The analysis windows for HIV, hematology, chemistry (including glucose), urinalysis, renal biomarkers, eGFRCG, vital signs, weight, CASI Follow-Up questionnaire, and DBS are presented in Table 3-1.

Table 3-1. Analysis Windows for HIV, Hematology, Chemistry, Urinalysis, Renal Biomarkers, eGFRCG, Vital Signs, Weight, CASI Follow-Up Questionnaire, and DBS

Visit ID	Nominal Day	Lower Limit	Upper Limit
Baseline	1	(none)	1
Week 4	28	2	56
Week 12	84	57	126
Week 24	168	127	210
Week 36	252	211	294
Week 48	336	295	378
Week 60	420	379	462
Week 72	504	463	546
Week 84	588	547	630
Week 96	672	631	714
Week 108	756	715	798
Week 120	840	799	882
Week K (K is every 12 weeks after previous visit)	K*7	(K-6)*7+1	(K+6)*7

HIV laboratory tests include both Covance central laboratory tests (HIV antibody screening tests, HIV Antibody Supplemental tests, qualitative and quantitative tests) and local laboratory tests (rapid HIV 1 Ag/Ab test or other local laboratory tests collected from eCRFs).

CASI follow up questionnaire collected at post baseline visits only, no baseline analysis window will be applied.

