### 6.2.2. Definition of HIV-1 Infection

HIV-1 infection is defined by one or more of the following criteria of contributing HIV tests performed via central lab or local lab:

- 1) Serologic evidence of seroconversion (reactive screening HIV Antigen/Antibody or Antibody test, confirmed by reactive HIV-1/HIV-2 differentiation assay), or
- 2) Virologic evidence of HIV-1 infection (positive qualitative HIV-1 RNA test or any detectable quantitative HIV-1 RNA test), or
- 3) Evidence of acute HIV-1 infection (reactive p24 Antigen or positive qualitative or quantitative RNA, in the absence of reactive HIV-1 Antibody results)

The flowchart in Figure 6-1 focuses on contributions from the central laboratory and provides a general assessment of contributing HIV tests performed by the central laboratory.

Figure 6-1. General Assessment of Contributing HIV tests Performed by the Central Laboratory

Positive virologic evidence, based on qualitative or quantitative HIV-1 RNA tests, is used for confirmation of HIV-1 infection while other HIV tests are also used to assess the date of diagnosis (ie, HIV infection date for analysis).

Positive virologic evidence is defined as either:

- 1) Qualitative HIV-1 RNA test with positive results or
- 2) Quantitative HIV-1 RNA test with detectable HIV-1 RNA results ("< 20 cp/ml HIV-1 RNA Detected" or any value ≥ 20 copies/mL)

The date of HIV infection diagnosis is assessed by a retrospective look, starting from the date of the first positive virologic evidence, through the preceding test results from other contributing HIV tests (including both Covance and local tests). The look back stops at the first date with negative assessments on all available HIV tests prior to the date of first positive virologic evidence. The date of HIV-1 diagnosis is set at the earliest positive result in the retrospective look process from either an on-site rapid test, a test sent to the central Covance laboratory, or any other provided local test performed outside of the study that documents the presence of HIV infection.

This algorithm excludes diagnosis of HIV-1 infection for vaccinated subjects who may have positive HIV-1 serology but no positive virologic evidence. For HIV vaccinated subjects, the date of HIV infection diagnosis is the date of first positive virologic evidence, based on qualitative or quantitative HIV-1 RNA tests.

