b) For a sensitivity analysis, the HIV infection incidence rate between F/TAF and F/TDF and its 95% exact CIs are calculated using the rate differences method. All references to 95% exact CIs are calculated using the method proposed by Ulm. The following SAS code will be used:

```
/*Hybrid CI*/
data test;
   alpha=0.025;
   zval = quantile("Normal", alpha);
   x1=42; *Number of HIV Infections in F/TAF arm;
   x2=101; *Number of HIV Infections in F/TDF arm;
   f1=500; *Total Person Years Follow Up in F/TAF arm;
   f2=400; *Total Person Years Follow Up in F/TDF arm;
    hat1 = x1/f1;
    hat2 = x2/f2;
    diff = hat1 hat2;
      /*Rate Difference: Hybrid CI*/
   11 quantile("CHISQ", alpha, 2*x1)/(2*f1); *Ulm lower exact CI;
   u1 quantile("CHISQ", 1-alpha, 2*x1+2)/(2*f1); *Ulm upper exact CI;
   12 quantile("CHISQ", alpha, 2*x2)/(2*f2); *Ulm lower exact CI;
   u2 quantile("CHISQ", 1-alpha, 2*x2+2)/(2*f2); *Ulm upper exact CI;
   hybriddifflower hat1 - hat2 - sqrt((hat1 - 11)**2 + (u2 - hat2)**2);
*Lower CI of Rate Difference (F/TAF-F/TDF);
   hybriddiffupper hat1 - hat2 + sqrt((hat1 - u1)**2 + (12 - hat2)**2);
*Upper CI of Rate Difference (F/TAF-F/TDF);
run;
```

d) The FAS and PP populations are based on HIV lab test results from either Covance or the Rapid HIV-1/2 Result (LB-HIVDX) eCRF, excluding the Other Local Labs eCRF.

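### SAP Appendix 12 item 16(d) bars outside local HIV tests from deciding FAS membership, although 3.1.2 and 6.2.2 accept them, so an infection shown only by a qualifying outside test is dropped

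*SAP*

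**What the plan says.** **Membership, as defined.** SAP 3.1.2, criterion (4), says that to contribute to the infection analyses a subject "should have at least one post-baseline HIV laboratory assessment (from either local or central laboratory"). The note to Table 3-1 (SAP 3.8.2) gives local HIV tests a wide meaning: "rapid HIV 1 Ag/Ab test or other local laboratory tests collected from eCRFs".

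**Membership, as programmed.** Appendix 12 item 16(d) bases the FAS and PP populations on HIV results from Covance or the on-site rapid result eCRF, "excluding the Other Local Labs eCRF".

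**Endpoint.** SAP 6.2.2 states that "HIV-1 infection is defined by one or more of the following criteria of contributing HIV tests performed via central lab or local lab". The look-back that dates the diagnosis may use "any other provided local test performed outside of the study that documents the presence of HIV infection". The same section adds a limit: "Positive virologic evidence, based on qualitative or quantitative HIV-1 RNA tests, is used for confirmation of HIV-1 infection". Item 16(e), directly after 16(d), sorts Other Local Labs results, qualitative and quantitative HIV-1 RNA among them, into positive and negative.

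**At-risk time.** SAP 3.8.1 ends follow-up for uninfected participants at the last test from a narrower list, "either local rapid or Covance HIV laboratory tests, including the 30-day follow-up visit date". SAP 6.2.3 speaks of local HIV tests without restricting them to rapid tests.

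**Disclosure.** SAP 6.3, which lists departures from the protocol's efficacy analyses, mentions only the dropped adherence criterion for the PP set. The protocol's FAS (8.2.1.2) requires randomization, dosing and no major violation, and has no post-baseline test requirement.

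**The concern.** The same eCRF is treated in two ways. For someone already in the FAS, an Other Local Labs result can establish or date an infection. For someone with no other post-baseline test, the same result cannot bring them into the FAS. A programmer who follows 16(d) produces a smaller population than 3.1.2 describes, and the text of the SAP does not reveal it.

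The people at risk of being lost are early drop-outs who were infected and tested elsewhere. The FAS carries the non-inferiority and superiority evaluation of the secondary efficacy endpoint (SAP 6.2.5). In a rate-ratio comparison with few events, a known infection left out of the F/TAF arm favours the non-inferiority claim, and one left out of the F/TDF arm works against it.

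**Working it through.** **Step 1. Follow one participant through the rules.** Take a person randomized and dosed, with a negative Day 1 rapid test, no further study visit, and a positive outside HIV-1 RNA recorded on the Other Local Labs eCRF.

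- 3.1.2 criteria (1) and (2), randomized and dosed: met.
- 3.1.2 criterion (3), not positive on Day 1: met through the negative Day 1 rapid test.
- 3.1.2 criterion (4), a post-baseline test from a local or central laboratory: met under the Table 3-1 meaning of local.
- 6.2.2, infection: met, because positive RNA is virologic evidence and local tests contribute.
- 16(d): not met. The person and the infection leave the FAS.

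Only 16(d) removes this person.

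**Step 2. Change the outside result.** If it is an antibody result without a differentiation assay, or a self-reported positive, 6.2.2 is not satisfied and no endpoint is lost. The conflict over membership remains, but no infection goes with it.

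**Step 3. Check the PP set.** SAP 3.1.3 already excludes anyone without a Covance antibody or HIV-1 RNA test between first dose and the date of diagnosis, because infection before first dose cannot be ruled out. The person in Step 1 fails that rule whatever 16(d) says.

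**Step 4. Scale.** SAP 1.3.1 gives 2500 per arm, 1.44 infections per 100 person-years in both arms, 2 years' average follow-up, a margin of 1.62 and two-sided alpha of 5%. These were set for the primary analysis and serve here only as a scale.

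- Planned events per arm: 2500 × 2 × 0.0144 = 72.
- SE of the log rate ratio: √(1/72 + 1/72) = 0.1667.
- Power: Φ(ln 1.62 / 0.1667 − 1.96) = 82.5%, which reproduces the stated figure of at least 82%.
- One infection as a share of one arm: 1/72 = 1.4%.

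The upper 95% limit is (x/y) × exp(1.96 × √(1/x + 1/y)), where x and y are the F/TAF and F/TDF infections. Equal person-years are assumed, and the short follow-up removed with one person is ignored.

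| Infections per arm | Upper limit, none lost | One F/TAF infection lost | One F/TDF infection lost |
|---|---|---|---|
| 72 (planned) | 1.386 | 1.369 | 1.407 |
| 30 (assumed) | 1.659 | 1.610 | 1.723 |
| 10 (per-group count in the case-control power calculation, SAP Appendix 9) | 2.403 | 2.215 | 2.734 |

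At the planned count one lost infection moves the limit by about 0.02. The 30-per-arm row was chosen because it lies close to the margin: there, losing one F/TAF infection takes the limit from above 1.62 to below it.

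**The case against.** **Local may have meant the on-site rapid test.** SAP 3.8.1 uses that narrower phrase. But 3.1.2 does not, 6.2.3 does not, and the Table 3-1 note is expressly wider. At the least the sections disagree.

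**The case is rare.** Rapid and central tests are scheduled at every post-baseline visit from Week 4, at early drug discontinuation and at the 30-day follow-up, and one such result is enough for membership. The affected person must have missed them all. This stands and limits the size of the point.

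**The infection may predate dosing.** This is true of someone with no study test after Day 1. However, the SAP handles that doubt by excluding such people from the PP set, not from the FAS.

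**Admitting outside tests could make inclusion depend on outcome.** This is the strongest objection. Protocol 6.11 asks sites to collect records from other clinics once infection is confirmed. There is no matching request for outside negative results from people who never return, so infected non-returners could enter while uninfected ones stay out. Restricting membership to study-collected tests is therefore defensible. But the SAP gives no such reason, and it does not state the restriction in 3.1.2 or 6.3.

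**Stronger readings that a reader might infer.** One is that 16(d) discards outside-documented infections generally. It does not: it governs membership, and outside results still contribute for anyone with a study test. Another is that any outside positive is an endpoint. 6.2.2 requires virologic evidence or a confirmed reactive test. A third is that the self-reported outside case in the footnote to item 16(e) is an affected participant. The test type there is unknown, and nothing says that person lacked study tests.

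**Conclusion.** The contradiction is real and narrow. Item 16(d) conflicts with 3.1.2, read with the Table 3-1 note, and with the sources accepted in 6.2.2. Its consequence for the endpoint is confined to randomized, dosed participants, negative on the Day 1 rapid test, whose only post-baseline result is an outside test that itself satisfies 6.2.2. For them the FAS loses both the person and the infection. The PP set is unaffected for this person.

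The documents give no count of such participants, and it is probably very small. At the planned 72 events per arm each one matters little (1.4% of an arm's events). With far fewer events each matters more. A reader might infer that the non-inferiority conclusion is in doubt. The documents do not support that, since no affected participant is identified and the only crossing of the margin shown above rests on an assumed count. The primary analysis had its own SAP, which is not among these documents, so nothing is claimed about it.

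**What to change.** Use a single list of accepted HIV test sources in SAP 3.1.2, 3.8.1, 6.2.3 and Appendix 12 item 16(d). Other Local Labs results, positive or negative, should then satisfy FAS criterion (4) and also define at-risk time. The at-risk rule has to change with the membership rule: otherwise someone admitted on an outside negative would have no end date under the wording of 3.8.1. Because outside tests may be reported mainly when positive, report the rate ratio both with and without participants who enter only through outside tests.

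If the sponsor prefers to keep the restriction, state it and its reason in 3.1.2 and 6.3. Add a sensitivity analysis that counts outside-documented infections meeting 6.2.2 among all randomized and dosed participants.

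Either route costs a few lines of specification, a change to the population program and one additional table. SAP 3.1 requires the set rules to be fixed before the blind is broken for analysis, and the study has already been unblinded once for the primary analysis. The change should therefore be made before the final unblinding, without reference to treatment arm, and entered in the SAP revision table.

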### 17) DXA Analysis:

- a) Variable used for analysis:
  - Variable CORRBMD when Region "SpineTotalAdequate" for spine, Region "FemurTotal" for hip, and Region "FemurNeck" for femur neck will be used for percentage change from baseline in BMD analysis.
  - Variable CORRTSCR\_M when Region "SpineTotalAdequate" for spine and Region "FemurTotal" for hip will be used for defining the BMD clinical status.
- b) ANOVA model for continuous variable: The differences in changes from baseline in BMD between treatment groups and the associated 95% CI will be constructed using an ANOVA, including baseline F/TDF for PrEP and treatment as fixed effects in the model.

```
proc glm data=adeff;
   class bftdf trtgrp;
   model BMD= bftdf trtgrp;
   lsmeans trtgrp /alpha=0.05 cl pdiff;
run;
```

c) For clinical BMD status, the following codes will be used to compute the p-values for comparing the two treatment groups using rank analysis of covariance adjusting for the baseline F/TDF for PrEP and baseline clinical BMD status:

```
proc rank data=BMD nplus1 ties=mean out=ranks;
  by bftdf;
  var BMDstatus Basestatus;
run;

proc reg data=ranks noprint;
  by bftdf;
  model BMDstatus=Basestatus;
  output out=residual r=resid;
run;

proc freq data=residual;
  tables bftdf * treatment * resid/noprint cmh2;
run:
```

d) For categories of percentage change from baseline in the hip BMD and spine BMD, the distribution difference in these categories (based on equidistant scores for each category) between the treatment groups will be compared using CMH test (row mean scores differ statistic) adjusting for baseline F/TDF for PrEP. SAS codes for treatment comparison will be:

```
proc freq order=data;
   tables bftdf * treatment * Y / cmh2; /*row mean score test*/
run;
```

18) For the distribution of UP and UPCR categories (or treatment-emergent proteinuria), the following codes will be used to compute the p-values for comparing the two treatment groups using rank analysis of covariance adjusting for baseline F/TDF for PrEP and baseline UP/UPCR categories:

```
proc rank data=UPCR nplus1 ties=mean out=ranks;
  by bftdf;
  var UPCRstatus Basestatus;
run;

proc reg data=ranks noprint;
  by bftdf;
  model UPCRstatus=Basestatus;
  output out=residual r=resid;
run;

proc freq data=residual;
  tables bftdf * treatment * resid/noprint cmh2;
run;
```

- 19) For prescribed adherence based on pill counts (Section 4.2.3.1), any bottles dispensed after the end date would not be counted into the adherence calculation.
- 20) LOCF and BIOCF will not be applied at a visit for a subject who is both missing on-treatment values at a visit and has not reached the upper limit of the analysis window for that corresponding visit. For the determination of whether a subject has reached the upper limit of the analysis window, the (1) lab transfer date for lab parameters or (2) DXA transfer date for BMD values will be compared to the upper limit of the analysis window.
- 21) For CASI summaries of
  - a) Adherence while on on-treatment (through the last dose date) includes all visits for subjects that are ongoing on study drug and visits occurring through the upper limit of the analysis window corresponding to the date of permanent discontinuation of study drug for subjects that permanently discontinued study drug. (ie. if the last dose date is Day 250, this falls in the Week 36 analysis window and all CASI visits through Day 294 will be included.)
  - b) Intercourse partners while at risk of HIV infection (through the last at-risk of HIV infection date) includes visits occurring through the upper limit of the analysis window corresponding to the last at-risk of HIV infection date for each subject.

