## 3. GENERAL CONSIDERATIONS FOR DATA ANALYSES

The end of blinded treatment phase analysis will include all data collected from the randomized and the open-label extension (OLE) phase of the study. Only data collected in the double-blinded (DB) phase (ie, DB phase data) will be summarized, if not specified otherwise. Data collected from both phases will be included in data listings.

A subject is considered to have enrolled in the open-label extension if the entry of OLENTRY form is 'yes'. The cutoff date of the OLE phase will be the date of first dose date of the OLE phase if it is available. If the subject is never dosed in the OLE phase, all available data are considered as the DB phase data.

For subjects who are not enrolled in the OLE phase, all available data are considered as the DB phase data. For subjects who are treated in the OLE phase, data collected up to the cutoff date will be considered as DB phase data, and data collected after the cutoff date will be considered as OLE phase data, except for adverse events (AEs), concomitant medications, and death. For AEs, concomitant medications, and death, data collected prior to the cutoff date are considered as DB phase data, and data collected on or after the cutoff date is considered OLE phase data.

Analysis results will be presented using descriptive statistics. In general for categorical (or ordinal) variables, the number and percentage of subjects in each category will be presented; for continuous variables, the number of subjects (n), mean, standard deviation (SD) or standard error (SE), median, first quartile (Q1), third quartile (Q3), minimum, and maximum will be presented.

All statistical tests will be 2-sided and performed at the 5% significance level unless otherwise specified.

By-subject listings will be presented for all subjects in the All Randomized Analysis Set and sorted by subject ID number, visit date, and time (if applicable), unless otherwise specified. Data collected on log forms, such as AEs, will be presented in chronological order within a subject. The treatment group to which subjects were randomized will be used in the listings. Age, MSM/TGW status, race, first dose date and HIV infection date will be included in the listings, as space permits.

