In general, permanent discontinuation of study drug refers to premature discontinuation of study drug or completion of study drug and regardless of any gaps in continuous dosing (ie, temporary discontinuation due to adverse event (AE) or subject request after which subjects may resume study drug).

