# The algorithm for LOCF is as follows:

- If a postbaseline value is missing in an analysis visit window, the missing value will be replaced with the last on-treatment value (ie, data collected up to 30 days after permanent discontinuation of study drug or all available data for subjects who were still on study drug) observed before the analysis visit window that has the missing value.
- Baseline values will be carried forward to impute the postbaseline value at a specific visit, if there is no nonmissing postbaseline observation collected prior to that visit.

The algorithm for BlOCF is as follows:

• Baseline values will be carried forward to impute the missing postbaseline value at a specific visit.

For missing or incomplete last dosing date of study drug, imputation rules are described in Section 3.8.1. For missing or incomplete start or end dates of study drug for the computation of study drug interruptions, imputation rules are described in Section 4.2.2.2. The handling of missing or incomplete dates for AE onset is described in Section 7.1.5.2, and for prior and concomitant medications in Section 7.6. Imputation rules for missing DBS concentration at the time of HIV diagnosis are as described in Appendix 9.

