# Appendix 9 Assessment of Adherence and Efficacy Based on Dried Blood Spot Concentration

#### DBS 1.1 Background

Drug exposure level has been identified as the key factor in optimizing efficacy of HIV-1 PrEP. Although drug exposure level is related to multiple factors, adherence to drug (consistent drug administration) is the most important factor.

Two substudies will be conducted:

- 1) Cohort substudy to estimate the overall rate of adherence
- 2) Case-Control substudy to assess the association of adherence with efficacy in the GS-US-412-2055 study

The GS-US-412-2055 study is a randomized double-blind comparison of the safety and efficacy of F/TAF versus F/TDF administered once daily (QD) for at least 96 weeks in HIV-1 negative adults to show noninferiority of F/TAF to F/TDF with respect to prevention of HIV-1 infection. The study is being conducted in 94 sites across 11 countries in both North America and Europe. Enrollment for the GS-US-412-2055 study began in September 2016 and ended in June 2017. The primary endpoint will be assessed when all subjects have a minimum follow-up of 48 weeks and at least 50% of the subjects have 96 weeks of follow-up after randomization or permanently discontinued from the study.

Cards with dried blood samples (DBS) should be placed in a freezer within 1 day after blood draw and should be stored frozen for optimal stability. Samples put in a freezer later than one day after blood has been drawn or those with missing date for placement in the freezer will not be considered for these substudies and will not be sent to the analytical laboratory.

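### The LOCF/BlOCF stopping rule runs on the data-transfer date, so planned completers can receive imputed renal values at post-Week-96 blinded visits they were never due to attend

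*SAP*

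**What the plan says.** SAP Section 3.6.1 names the endpoints to be imputed by LOCF and BlOCF: hip and spine BMD, the two urine marker ratios, UP/UPCR categories and serum creatinine. It states no visit limit. Under LOCF, "the missing value will be replaced with the last on-treatment value" seen before the empty window. Under BlOCF, "Baseline values will be carried forward to impute the missing postbaseline value at a specific visit".

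The only stopping rule is Appendix 12 item 20: "LOCF and BIOCF will not be applied at a visit for a subject who is both missing on-treatment values at a visit". A second condition must hold as well: that visit's window must still be open. Whether it has closed is judged by calendar: the "lab transfer date for lab parameters or (2) DXA transfer date for BMD values will be compared to the upper limit".

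Three other provisions decide how this works for a planned completer:

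- Section 3 sets the end of blinded data at the first open-label dose: "For subjects who are treated in the OLE phase, data collected up to the cutoff date will be considered as DB phase data".
- Section 3.8.2 says that open-label observations "will not have analysis window assigned and will be included in listings with derived visit marked as" Extension, so they cannot fill a blinded window.
- Section 3 also says that "permanent discontinuation of study drug refers to premature discontinuation of study drug or completion of study drug". A completer's on-treatment period therefore ends at completion. That limits which values may be carried forward, not the windows they may be carried to.

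**The concern.** A transfer-date clock suits a data cut in an ongoing study, where it separates visits that are still to come from visits that were missed. It does not suit an analysis run after the blinded phase has closed. Participants stay blinded until the last one reaches Week 96 (SAP Section 1.2), so planned blinded follow-up differs with enrolment date. Early enrollees have real data in the Week 108, 120 and 132 windows. Late enrollees stopped at about Week 96 by design, and their later windows are empty because no visit was due. Once the transfer date passes the upper limit of such a window, item 20 no longer blocks imputation. BlOCF then enters zero change and LOCF repeats the last value.

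The next item in Appendix 12, item 21, caps the CASI summaries at each participant's own discontinuation or last at-risk date. Item 20 has no comparable participant-level stop. At stake is the meaning of the post-Week-96 sensitivity summaries. They would mix handling of missing data with values invented for planned completers, in a proportion set by an administrative date.

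**Working it through.** **Window limits.** Table 3-1 gives the general rule for Week K as (K−6)×7+1 to (K+6)×7. For Weeks 96, 108 and 120 this gives 631–714, 715–798 and 799–882, which matches the table rows. By the same rule Week 132 is 883–966. Table 3-5 gives DXA Week 96 as 505–840 and Week 144 as 841–1176, with no upper limit after that.

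**Laboratory gap.** Let a completer's EOB fall on Day d in window K, and let the transfer come T days later, on Day d+T. The next window is over-imputed once d+T ≥ (K+18)×7.

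- EOB on the last day of window K: gap = (K+18)×7 − (K+6)×7 = 84 days.
- EOB on the nominal day: gap = (K+18)×7 − 7K = 126 days.
- EOB on the first day of window K: gap = 83 + 84 = 167 days.

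No completer is affected before 84 days, and every completer is affected from 167 days.

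**Assumptions for the shares.** "Enrollment for the GS-US-412-2055 study began in September 2016 and ended in June 2017"; I take this as 36 to 43 weeks of uniform accrual. EOB is a single calendar date, 0 or 12 weeks after the last participant's Week 96. Day d is then spread evenly over 253 days (36×7+1) or 302 days (43×7+1), starting at Day 672 or Day 756. The transfer date is not in the documents, so T is varied.

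| T after EOB | Affected days per 84-day window | Accrual 36 weeks (3 windows) | Accrual 43 weeks (4 windows) |
|---|---|---|---|
| ≤60 days | 0 | 0% | 0% |
| 90 days | 7 | 21/253 = 8.3% | 28/302 = 9.3% |
| 120 days | 37 | 111/253 = 43.9% | 148/302 = 49.0% |
| 180 days | all | 100% | 100% |

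An EOB date 6 weeks after the last Week 96 aligns differently with the windows. It gives 7–9% at 90 days and 38–44% at 120 days.

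**DXA Week 144.** A completer lacks a Week 144 scan only if EOB is on or before Day 840. Item 20 then allows imputation once d+T ≥ 1176, so the gap is at least 1176 − 840 = 336 days. At T = 270 the share is 0%. At T = 365, d must lie in Days 811–840, which is 30 days: 30/253 = 11.9% or 30/302 = 9.9%. An EOB scan on or after Day 841 already falls in the Week 144 window or later.

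**If EOB visits are staggered.** The EOB visit may coincide with the next scheduled visit. Taking Day 1 as uniform from 15 September 2016 to 15 June 2017, EOB at the next 12-weekly visit, and time counted from the *last* EOB visit, the laboratory shares are 0% at 30 days, 20% at 60, 53% at 90, 91% at 120 and 100% at 180. DXA is 0% up to 180 days, 7% at 270 and 41% at 365. These are higher because most participants' own EOB comes before the last one.

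**The case against.** The strongest reply is that Section 3.6.1 imputes the secondary endpoints, and the protocol defines those only at Weeks 48 and 96. On that reading no LOCF/BlOCF table exists after Week 96. This is arguable, but the SAP does not say it. Section 3.6.1 names the endpoints without visits, item 20 speaks of any visit, and Sections 7.4.1 and 7.4.4 summarise the renal ratios and creatinine by visit. For UP/UPCR the reply holds: Section 7.4.2 and the table shell are limited to Weeks 48 and 96.

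It is also true that LOCF and BlOCF are sensitivity analyses. The specified treatment comparisons use observed on-treatment data.

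A reader might go further and infer that the transfer date is bound to fall after every blinded window, that all completers without data in a later window are imputed, that BMD is affected, or that imputed values dominate the late visits. The documents support none of these. They give no transfer date. Counting completers without data in a window tests only its lower limit, whereas item 20 also needs the transfer to pass the upper limit, so such counts are ceilings. For DXA Week 144 the ceiling is 28–67%, against 0% through 270 days once a transfer date is applied to a common EOB date.

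**Conclusion.** The defect is real but minor. The rule as written can impute values at post-Week-96 laboratory visits that planned completers were never due to attend, and how often depends on an unstated date. With a common EOB date and uniform accrual of 36 to 43 weeks, a transfer within 60 days affects no one, one at about four months affects close to half of completers, and one at six months affects all of them.

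The material exposure is the LOCF/BlOCF summaries of urine RBP and beta-2-microglobulin ratios and serum creatinine after Week 96, if those tables are produced. BlOCF would add zero changes there and pull arm differences toward zero. A BMD effect is not shown. The alpha-controlled Week 48 endpoints, the Week 96 endpoints, the UP/UPCR tables and all observed-data comparisons are unaffected.

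**What to change.** Either of two changes is enough.

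1. State in Section 3.6.1 that LOCF and BlOCF are applied at Weeks 48 and 96 only. This is the simpler choice and matches the protocol's endpoints.
2. Amend item 20 so that neither method is applied at any window whose lower limit falls after a planned completer's blinded phase ended (EOB visit or first open-label dose). State the rule for premature discontinuers separately.

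The bar must use the window's lower limit. Using the upper limit would block imputation of a genuinely missed Week 96 value when EOB falls on Days 672–713 for laboratory data or Days 672–839 for DXA.

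The cost is one sentence, plus one date comparison in the program for the second option. Imputation at Weeks 48 and 96 is unchanged, and planned completers' results no longer depend on when the data were transferred.
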